3.0 Study Plan and Overview

3.0 Study Plan and Overview

76 breast cancer patients with malignant pleural effusion will be recruited and treated with VPA or placebo for 10 weeks. Prior data suggest chronic low dose administration is ideal for HDAC inhibition. Since q3wk dosing has often been given an average of 4 cycles, 12 weeks, 10 weeks of daily treatment is in this range and is long enough to examine fluid at multiple endpoints while on treatment while minimizing the side effects and cost of the trial.

MD Anderson Cancer Center's IND office will provide monitoring for this protocol. Patients, the investigator and the research monitor will be blinded to treatment randomization.

3.1 Timeline

In the first two years of the proposed project, we will conduct the clinical trial and collect samples and information. Biological correlates and data analysis will be performed on fresh samples as the trial proceeds.

3.2 Patient Recruitment

Patients will be recruited for this study by working closely with Breast Medical Oncologists. Representatives from Radiation Oncology, Breast Medical Oncology and Pulmonary Medicine (i.e., the principal investigator, the co-principal investigator, co-investigators, and the research nurse) will screen and evaluate patients seen in the MD Anderson Breast Center to identify potential subjects.

When medically appropriate, catheters will be placed as per standard of care by a pulmonologist or their trained designee after signing the usual consent for this procedure. Monitoring will be standard of care as directed by the MD responsible for

placing the catheter.

3.3 Pretreatment Evaluations

Patients deemed to require catheter placement based on standard of care algorithms and gleaned from the Electronic Medical Record, will be screened for protocol eligibility. (See Section 4.0) When medically appropriate, catheters will be placed as per standard of care by a pulmonologist or their trained designee after signing the usual consent for this procedure. Monitoring will be standard of care as directed by the MD responsible for placing the catheter.

Unless otherwise noted, labs, physical exams, and screening are to be performed within 7 days of enrollment. Imaging studies are to be performed within 30 days of enrollment.

- 3.3.1 Sign an informed consent.
- 3.3.2 Complete physical exam, including measurement of vital signs, performance status, weight and medical history
- 3.3.3 Pretreatment laboratory tests:
 - **Hematology:** CBC with differential
 - **Chemistry:** Electrolytes, BUN, creatinine, glucose, albumin, alkaline phosphatase, ALT or AST, LDH, total bilirubin, amylase, lipase, magnesium and ionized calcium.
 - **Coagulation:** Prothrombin time (PT), partial thromboplastin time (PTT), and International Normalized Ratio (INR).
 - **Serum or Urine Pregnancy test:** Required for females of child-bearing potential. Documented use of contraception, sexual abstinence, or amenorrhea for > 6 months is sufficient to document patient is not of child-bearing potential. Otherwise must be obtained prior to first dose of VPA and must be negative to enroll.
- 3.3.4 EQ-5D and St. George's respiratory questionnaire
- 3.3.5 Chest x-ray within 72 hours prior to catheter placement.
- 3.3.6 Chart will be reviewed for re-staging CT scan of the chest. One will be ordered if not performed since the development of the effusion.

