1.2.2 Safety Profile for VPA

Frequency of adverse effects by organ system:

>10%:

Central nervous system: Headache (>31%), somnolence (>30%), dizziness (12% to 25%), insomnia (>1% to 15%), nervousness (>1% to 11%), pain (1% to 11%)

Dermatologic: Alopecia (>1% to 24%)

Gastrointestinal: Nausea (15% to 48%), vomiting (7% to 27%), diarrhea (7% to 23%), abdominal pain (7% to 23%), dyspepsia (7% to 23%), anorexia (>1% to 12%)

Hematologic: Thrombocytopenia (1% to 24%; dose related)

Neuromuscular & skeletal: Tremor (>57%), weakness (6% to 27%)

Ocular: Diplopia (>1% to 16%), amblyopia/blurred vision (>12%)

Miscellaneous: Infection (>20%), flu-like syndrome (12%)

1% to 10%:

Cardiovascular: Peripheral edema (>1% to 8%), chest pain (>1% to <5%), edema (>1% to <5%), facial edema (>1% to <5%), hypertension (>1% to <5%), hypotension (>1% to <5%), palpitation (>1% to <5%), postural hypotension (>1% to <5%), tachycardia (>1% to <5%), vasodilation (>1% to <5%), arrhythmia

Central nervous system: Ataxia (>1% to 8%), amnesia (>1% to 7%), emotional lability (>1% to 6%), fever (>1% to 6%), abnormal thinking (>6%), depression (>1% to 5%), abnormal dreams (>1% to <5%), agitation (>1% to <5%), anxiety (>1% to <5%), catatonia (>1% to <5%), chills (>1% to <5%), confusion (>1% to <5%), coordination abnormal (>1% to <5%), hallucination (>1% to <5%), malaise (>1% to <5%), personality disorder (>1% to <5%), speech disorder (>1% to <5%), tardive dyskinesia (>1% to <5%), vertigo (>1% to <5%), euphoria (1%), hypoesthesia (1%)

Dermatologic: Rash (>1% to 6%), bruising (>1% to 5%), discoid lupus erythematosus (>1% to <5%), dry skin (>1% to <5%), furunculosis (>1% to <5%), petechia (>1% to <5%), pruritus (>1% to <5%), seborrhea (>1% to <5%)

Endocrine & metabolic: Amenorrhea (>1% to <5%), dysmenorrhea (>1% to <5%), metrorrhagia (>1% to <5%), hypoproteinemia

Gastrointestinal: Weight gain (4% to 9%), weight loss (6%), appetite increased

(·6%), constipation (>1% to 5%), xerostomia (>1% to 5%), eructation (>1% to <5%), fecal incontinence (>1% to <5%), flatulence (>1% to <5%), gastroenteritis (>1% to <5%), glossitis (>1% to <5%), hematemesis (>1% to <5%), pancreatitis (>1% to <5%), periodontal abscess (>1% to <5%), stomatitis (>1% to <5%), taste perversion (>1% to <5%), dysphagia, gum hemorrhage, mouth ulceration

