4.0 Patient Eligibility

4.0 Eligibility Criteria

4.1 Inclusion Criteria

- Patients with symptomatic pleural effusion requiring placement of an IPC.
- Pathologic documentation of breast cancer.
- Performance status 0 to 3 (ECOG scale).

- 4.1.4 Signed informed consent prior to the indwelling pleural catheter placement.
- 4.1.5 Subject must be female or male age 18 years or over.
- 4.1.6 At least one prior line of chemotherapy in the metastatic setting
- 4.1.7 Positive effusion cytology

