4.2.20 History of seizures

4.3 Restrictions

Because of the teratogenic nature of VPA, female patients must be six months postmenopausal, surgically sterile, or using an acceptable method of contraception. Female patients must agree to continue using an acceptable method of contraception for a period of three months after study medication administration. Acceptable methods of contraception are oral contraceptives, barrier methods, approved contraceptive implant, long-term injectable contraception, intrauterine device or tubal ligation.

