5.1.5 Precautions for Treatment

VPA should not be administered to pregnant women. A negative pregnancy test should be confirmed before administration of VPA.

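### Section 3.3.3 and Study Parameters footnote 1 waive the pre-dose pregnancy test for women on documented contraception, in conflict with 5.1.5 and with the reasoning of 4.3

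*Combined protocol and SAP*

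**What the plan says.** The screening rule stands in 3.3.3 and is repeated in footnote 1 of the Study Parameters table. It limits the pregnancy test to women of child-bearing potential and then names three grounds for placing a woman outside that group: "Documented use of contraception, sexual abstinence, or amenorrhea for > 6 months is sufficient to document patient is not of child-bearing potential". The test is compulsory only for the rest: "Otherwise must be obtained prior to first dose of VPA and must be negative to enroll".

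Three other parts of the protocol bear on the same question.

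- Section 4.3 cites the teratogenicity of VPA and requires that "female patients must be six months postmenopausal, surgically sterile, or using an acceptable method of contraception". It lists the methods it accepts: "Acceptable methods of contraception are oral contraceptives, barrier methods, approved contraceptive implant, long-term injectable contraception, intrauterine device or tubal ligation".
- Section 5.1.5 says: "A negative pregnancy test should be confirmed before administration of VPA". The sentence recurs twice in section 7, under 7.0 and again after 7.2.
- Section 4.2.8 excludes women who are pregnant.

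**The concern.** Contraception is required of a woman because she could conceive. Section 3.3.3 takes the same fact as showing that she could not, and drops her test for that reason. The drug carries a boxed warning for fetal harm (1.2.2 and 5.1.4), and pregnancy is an exclusion, so the pretreatment test is the laboratory check on that exclusion. If it is skipped, an early pregnancy that history and examination miss would be exposed to VPA. What is at stake is patient safety and the enforceability of 4.2.8. No statistical quantity in the plan depends on it.

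**Working it through.** There is no figure in the plan to reproduce and no arithmetic to do. The check sets the sections side by side.

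1. **Can a fertile woman enroll?** Yes. Inclusion 4.1.5 reads "Subject must be female or male age 18 years or over", with no menopausal limit. Section 4.3 offers women three routes: postmenopausal, surgically sterile, or on accepted contraception. A fertile woman enters by the third.

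2. **What does 3.3.3 do with her?** If her contraception is documented, she is classed as not of child-bearing potential. The compulsory test applies only to women who meet none of the three grounds, so she is not tested. Footnote 1 gives the same result, and the table row marks the test as applying only where relevant.

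3. **Does the six-month phrase rescue the rule?** It can be read in two ways.
   - If it qualifies amenorrhea alone, documented contraception of any duration waives the test.
   - If it qualifies all three grounds, contraception must have lasted more than six months. A fertile woman who meets that is still waived.

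4. **Does 5.1.5 agree with 3.3.3?** No. For this woman 5.1.5 asks for a negative test before VPA, and 3.3.3 says that none is needed. Nothing in the protocol says which section takes precedence.

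5. **Is there a later check?** The Study Parameters table schedules the pregnancy test only before catheter placement and shows none at weeks 2, 6 or 10. Under 3.4, study drug starts on the day of placement if cytology is positive. Section 5.3.2 stops the drug after a positive hCG, but no on-treatment test is scheduled that would find one.

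6. **The other two grounds.**
   - Abstinence is not among the methods in 4.3, so a fertile woman relying on abstinence alone does not meet 4.3. The abstinence waiver is a mismatch of wording more than a separate route to untested dosing.
   - For amenorrhea, 3.3.3 speaks of more than six months without periods, while 4.3 speaks of being six months postmenopausal. The two terms differ and should be made one.

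**The case against.** The best reply is that the protocol already covers this. Section 5.1.5 states the precaution three times without exemption, 4.2.8 excludes pregnant women, and a site that applies the whole document would test before dosing. That has force, and it makes the defect a conflict between sections rather than a missing safeguard. It does not remove the defect. Section 5.1.5 is worded as advice, while 3.3.3 and footnote 1 are the instructions that screening staff work from, and they say that the test is unnecessary.

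A reader might infer more than the documents support, in five ways.

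- **That 4.3 states the opposite of 3.3.3.** Section 4.3 neither defines child-bearing potential nor mentions testing. The conflict with it is one of reasoning; the direct conflict is with 5.1.5.
- **That the amenorrhea ground fails because VPA or chemotherapy stops periods.** Amenorrhea is listed as an effect of VPA in 1.2.2, but the waiver concerns amenorrhea present at screening, and 4.2.17 excludes patients currently taking VPA. As to chemotherapy, 4.1.6 says only "At least one prior line of chemotherapy in the metastatic setting". No section says that such treatment causes amenorrhea in women who stay fertile.
- **That the compulsory test would almost never be done.** That depends on how many women have contraception on record, and on which reading of the six-month phrase applies. The documents settle neither.
- **That the scope can be put as a fraction.** Counting combinations of contraception record and menstrual status gives a figure that changes with how the categories are cut and carries no weights. It measures nothing about patients.
- **That 8.3 concedes contraceptive failure.** It concerns possible interference of the study product with a contraceptive, and decides nothing about who is tested at screening.

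The provisions for pregnancy on study (5.3.2 and 8.3) limit harm after exposure. They do not prevent it.

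**Conclusion.** The point holds as a correctable error in the screening text. Section 3.3.3 and footnote 1 are wrong as written in treating documented contraception, and abstinence with it, as evidence that a woman cannot be pregnant. They conflict openly with 5.1.5 and by implication with 4.3. Following them can lead to VPA being started in an untested fertile woman, with no scheduled test afterwards.

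The size cannot be given. The documents hold no age or menopausal breakdown of the expected patients, and the number of women affected may be small. The conclusion assumes only that some fertile women enroll, as 4.1.5 and 4.3 permit, and that some sites act on the screening text rather than on 5.1.5. It should be changed on grounds of patient safety. Sample size, power and the primary analysis are unaffected.

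**What to change.** In 3.3.3 and in footnote 1:

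- Delete contraception and abstinence as grounds for waiving the test.
- Require a negative serum or urine pregnancy test, within 7 days of enrollment and before the first dose, for every woman who is not postmenopausal or surgically sterile as in 4.3, whatever her contraception.
- Replace the bare amenorrhea ground with the term used in 4.3, six months postmenopausal, so that both sections use one term. The protocol does not define that term, so a one-line criterion would help sites apply it.
- Say that tubal ligation counts as surgical sterility for this rule, since 4.3 lists it among contraceptive methods.

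Section 5.1.5 and its repeats can stay as they are. After the change, the only remaining difference from 3.3.3 concerns women who are postmenopausal or sterile.

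The cost is a wording change in two places and at most one extra urine or serum test per affected woman, with the result in hand before dosing on the day of catheter placement. The test and its 7-day window are already in the schedule.

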3.4 On-Study Evaluations

On the day of indwelling intrapleural catheter placement the patient's pleural fluid will be drained, recorded and sent for cytology review. On the day of indwelling intrapleural catheter placement patients will receive VPA or **placebo** if cytology is positive. Patients will be provided a diary to record drainage from home.

Patients will be treated for the whole period of 10 weeks, and clinical course of disease will be monitored throughout this time. (Note: evaluations may be done within \pm 7 business days of the date specified in the protocol).

Patients will initially receive daily oral VPA 15 mg/kg/day divided in three doses or placebo divided in three doses. Based on the patient's bmi, obese patient dosing will be based on the adjusted body weight calculated using the MD Anderson Clinical

Calculator Formula (<http://inside2.mdanderson.org/apps/calculators/calc1.cfm>). If the patient tolerates the reduced dose for 10 consecutive days then the VPA dose will increase to 30 mg/kg/day divided into three doses or placebo divided into three doses. The patient will be contacted by phone to assess tolerance and instruction to increase dose. Daily dose in mg will be divided by 250 mg and rounded down to a whole number of capsules to determine the number of VPA tablets or placebo tablets to be taken 3 times per day.

Evaluations may occur any time during weeks 2, 6, and 10.

- 3.4.1 Patients will document daily amount of pleural fluid drainage.
- 3.4.2 Patients will be evaluated at weeks 2, 6, and 10 with complete interim histories and physical examinations including measurement of vital signs, performance status, weight and medical history.
- 3.4.3 Patients will complete a EQ-5D and St. George's respiratory questionnaire, at weeks 2, 6, and 10 in person, via telephone or electronic media.
- 3.4.4 Blood samples for CBC with differential, platelet count, and PT/PTT/INR, serum and plasma banking, and optional CTC (if patient agrees) assessment will be collected prior to treatment and at weeks 2, 6 and 10.
- 3.4.5 Tests to measure serum electrolytes, BUN, creatinine, glucose, albumin, alkaline phosphatase, AST or ALT, LDH, total bilirubin, amylase, lipase, magnesium and ionized calcium will be performed at weeks 2, 6, and 10.
- 3.4.6 Optional urine (if patient agrees) will be collected prior to treatment and at weeks 2, 6 and 10.
- 3.4.7 Chest x-ray will be performed immediately after catheter placement and at weeks 2, 6, and 10.
- 3.4.8 CT scan will be performed at week 10 or earlier, if clinically indicated, to determine amount of effusion and drug effect on tumor burden.
- 3.4.9 Pleural effusion will be collected at each clinic visit. Residual fluid may be stored for additional research studies (optional).

On-Study Evaluations beyond Week 10

The EQ-5D, St. George's respiratory questionnaire and the obtaining of pleural fluid samples for research purposes will cease at the end of Week 10. After the completion of 10 weeks of VPA or placebo the patient's medical record will be followed for the date of catheter removal or date of death, which ever comes first.

Study Parameters

Studies	Prior to catheter placement	Within 72 hours prior to catheter placement	Day of catheter placement	Weeks 2, 6 and 10*	Week 10	Review EMR
Physical Exam including: v/s, wt	X ³			X ³		
Medical History	X			X		
Pregnancy Test if applicable	X ^{1,3}					
Ionized Calcium	X ³					
Magnesium	X ³					
Bloodwork	X ^{2,3}			X ^{2,3}		
ECOG PS	X			X		
St. George's questionnaire	X ³			X ³		
EQ-5D	X ³			X ³		
CXR PA and LAT		X	X	X		
Patient daily documentation of pleural fluid drainage			X	X		
Patient daily documentation of VPA or placebo administration			X	X		
optional pleural fluid			X	X		
optional blood			X	X		
optional urine			X	X		
CT chest	X ⁴				X	
Serum valproic acid for grade 2 or greater AEs ⁵						
Date of pleural catheter removal or death date						X

- Serum or Urine Pregnancy test:** Required for females of child-bearing potential. Documented use of contraception, sexual abstinence, or amenorrhea for > 6 months is sufficient to document patient is not of child-bearing potential. Otherwise must be obtained prior to first dose of VPA and must be negative to enroll.
- Hematology: CBC with differential Chemistry:** Electrolytes, BUN, creatinine, glucose, albumin, alkaline phosphatase, ALT or AST, LDH, total bilirubin, amylase, lipase, magnesium and ionized calcium.
Coagulation: Prothrombin time (PT), partial thromboplastin time (PTT), and International Normalized Ratio (INR) at baseline only.
- Within 7 days of enrollment
- Baseline CT chest completed after development of effusion and within 4 weeks of enrollment.
- Draw serum valproic acid level for any grade 2 or greater adverse events.
- Evaluations may occur any time during weeks 2, 6, and 10.

* If the patient tolerates the reduced dose for 10 consecutive days then the VPA dose will increase. This will be assessed at the 2 week visit. The patient will be contacted by phone to assess tolerance and instruction to increase the dose.

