2.3 Secondary Objectives

- 2.3.1 Measure the amount of pleural fluid drainage.
- 2.3.2 Study expression of inflammatory cytokines using the Luminex platform and the degree of H3 and H4 hyperacetylation in serum and pleural effusion cells.
- 2.3.3 Evaluate the effect of the study agent on tumor burden with chest CTs.
- 2.3.4 Evaluate the effect of the study agent on symptom burden, dyspnea and exercise tolerance
- 2.2.5 Measure level of circulating tumor cells in peripheral blood and pleural effusion.
- 2.2.6 Study expression of cancer stem cell markers on tumor cells in pleural effusion.
- 2.2.7 Record treatment related toxicity.
- 2.2.8 Record overall survival
- 2.2.9 Obtain urine samples for correlative studies

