7.1 Criteria for Intrapleural Catheter Removal

If a patient experiences the following criteria:

Once the amount of daily drainage is ≤ 150 ml for three consecutive days, pleural fluid will be drained every other day. While draining every other day, if the amount of fluid increases > 150 ml, daily drainage will be restarted. If the amount of fluid drained every other day is ≤ 150 ml on three consecutive occasions (total of 6 days), patients will be evaluated clinically and with chest radiographs and the indwelling intrapleural catheter will be removed if there is no evidence of fluid reaccumulation.

Treatment failure:

A. Patients meeting the criteria below will be considered failures as they require

removal of their catheters:

- Death while catheter in place.
- Fluid loculation with a non functioning catheter that does not meet the definition of pleurodesis.
- Blockage of IPC requiring removal of the catheter. Blockage of IPC not requiring removal but use of any unblocking therapeutic manouvers will be documented as a complication but not considered as treatment failure.
- Infection - tunnel infection, empyema or systemic infection. Exit site infection

will be reported as complication but not as a treatment failure unless it progresses to tunnel infection, empyema or systemic infection.

- Intractable pain.
- Dislodged cuff requiring removal of the catheter.

B. IPC in place >180 days without meeting catheter removal criteria.

C. Any other IPC removal that does not meet the criteria established in the treatment plan.

D. Non compliance.

E. Secondary failure. Patients requiring any additional procedure to remove pleural fluid from the affected hemithorax, to alleviate respiratory symptoms during the first 6 months after IPC has been removed following the treatment plan guidelines.

Symptomatic pleural effusion was defined as the radiological presence of pleural fluid regarded as the cause of the dyspnea by the treating physician.

Time to pleurodesis was calculated as the days between IPC insertion and removal.

Adequate lung re-expansion is defined as at least 80% pleurae apposition on the affected hemithorax as determined by visual estimation on radiological studies of the chest while IPC is in place.

Unexpandable lung (non-reexpandable lung) is the inability of the lung to expand to the chest wall allowing for normal visceral and parietal pleural apposition. The lung could be trapped or entrapped.

Pleurodesis

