- A. **Successful pleurodesis:** After IPC removal, long term relief of symptoms related to effusion with absence of fluid reaccumulation on chest radiographs for the remainder of the patients life or until last follow up (6 months after IPC removal).
- B. **Partially successful pleurodesis:** After IPC removal, diminution of dyspnea related to the effusion, with 50% or less reaccumulation of fluid when compared to pre-procedure chest radiographs but without the need for further therapeutic thoracentesis for the remainder of the patients life or until last follow up (6 months after IPC removal)

IPC related infections are defined as follows:

- A. **Local infection** - temperature <38 °C, no rigors, no purulent pleural fluid, no evidence of systemic infection. Local infections are divided in:
 - i. Exit site infection - erythema, tenderness and induration only at the exit site.

- ii. Tunnel infection - erythema, tenderness and induration overlying tunnel tract, and extending more than 2 cm from exit site.
- B. **Empyema or systemic infection** - fever > 38 C or rigors, purulent pleural fluid or evidence of systemic infection.

Other complications during or after a pleural procedure were defined as:

- A. Bleeding causing hemodynamic derangement or requiring blood transfusion.
- B. Presence of pneumothorax.
- C. Persistent ipsilateral chest pain after IPC insertion

Catheter obstruction - catheter blockage requiring removal with an additional palliative procedure.

Non Compliance - patient's inability or refusal to comply with study procedure after documented counseling.

Completion of Study - > 180 days with catheter in place, > 180 days after removal of IPC, or considered a treatment failure.

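### Record follow-up ends at catheter removal, which contradicts the 6-month post-removal outcomes in 7.1 and leaves overall survival without follow-up after removal

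*Combined protocol and SAP*

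**What the plan says.** Section 3.4, under the heading for evaluations beyond week 10, says that once the 10 weeks of study drug are complete the "medical record will be followed for the date of catheter removal or date of death, which ever comes first". The Study Parameters table agrees: the only row marked under record review is "Date of pleural catheter removal or death date".

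Section 7.1 uses a longer horizon. A secondary failure is a patient who needs a further procedure to remove fluid "to alleviate respiratory symptoms during the first 6 months after IPC has been removed following the treatment plan guidelines". Successful and partially successful pleurodesis are judged up to death or to a last follow-up 6 months after removal. The end of the study for a patient is "Completion of Study - > 180 days with catheter in place, > 180 days after removal of IPC, or considered a treatment failure".

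Section 2.3 lists "Record overall survival" as a secondary objective (item 2.2.8), and the third aim in 2.1 also names survival. Section 6.0 gives no definition, censoring rule or analysis for it.

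**The concern.** A record that is closed at catheter removal cannot show whether the fluid came back in the next 6 months, so the outcomes defined in 7.1 could not be ascertained by following 3.4.

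The effect on survival is separate. The end of survival follow-up would be set by the primary event. If valproate does what the trial hopes, catheters come out sooner on that arm and survival follow-up is shorter there. Any summary of survival by arm would then rest on unequal observation.

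Survival information is worth having here. Section 1.1 notes that, under the cancer stem cell hypothesis, the laboratory findings would imply a worse outcome on valproate, and then cites clinical data pointing the other way. A randomised placebo comparison is a good place to collect deaths completely.

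**Working it through.** The plan states no number of expected deaths and no length of survival follow-up, so there is no figure to reproduce. The contradiction itself is textual. The arithmetic below only sizes the effect on survival.

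**Inputs**
- Median survival with malignant effusion from breast cancer: 7.4 months (1.1), about 225 days.
- Removal medians (6.0): 56 days control and 28 days active; alternatively 110 and 55 days. Preliminary median 110 days, 95% CI 56 to 328.
- 76 patients, 38 per arm, 3 enrolled per month (6.0).
- Visits at weeks 2, 6 and 10 (3.4), so deaths to day 70 are taken as seen whether or not the catheter is out.
- Death is a serious adverse event, captured to 30 days after the last dose (8.1): about day 100 if all 10 weeks are taken.
- Assumption: times to removal and to death are independent and exponential.

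**Step 1: death before removal.** With λd = ln 2/225.2 = 0.00308 per day and λr = ln 2/(removal median), P(death first) = λd/(λd + λr).

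**Step 2: add deaths after removal but by day w.** P(removal first, death by w) = (1 − exp(−λd·w)) − P(death first) × (1 − exp(−(λd + λr)·w)).

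| Removal median | Death first | Death seen, w = 70 | Death seen, w = 100 |
|---|---|---|---|
| 56 days | 0.199 | 0.261 | 0.307 |
| 28 days | 0.111 | 0.210 | 0.272 |
| 110 days | 0.328 | 0.364 | 0.393 |
| 55 days | 0.196 | 0.259 | 0.306 |

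**Step 3: deaths recorded among 76.**
- Medians 56/28: 38 × (0.261 + 0.210) = 17.9 with w = 70; 38 × (0.307 + 0.272) = 22.0 with w = 100.
- Medians 110/55: 38 × (0.364 + 0.259) = 23.7; 38 × (0.393 + 0.306) = 26.6.

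These counts put no end date on patients whose catheter stays in, which favours the plan.

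**Step 4: comparator.** Accrual lasts A = 76/3 = 25.3 months. With λ = ln 2/7.4 = 0.0937 per month and a cut-off f months after the last enrolment, the share dead is 1 − [exp(−λf) − exp(−λ(A + f))]/(λA).
- f = 3: 1 − (0.755 − 0.070)/2.373 = 0.711, or 54 of 76.
- f = 6: 1 − (0.570 − 0.053)/2.373 = 0.782, or 59 of 76.

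**Step 5: dependence on arm.** Crediting deaths to week 10, the share of deaths unseen is 79% active against 74% control (28 and 56 days), or 74% against 64% (55 and 110 days). Both contrasts require the hazard ratio of 2.0 to be true.

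**Step 6: sensitivity.** With median survival of 4 to 12 months and either pair of removal medians, the share of deaths unseen after week-10 credit runs from 53% to 85%. At a removal median of 328 days it falls to 39%.

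**Step 7: would alignment with 7.1 be enough?** With follow-up to 180 days after removal, P(death seen) = P(death first) + P(removal first) × (1 − exp(−180λd)). That averages 51% (39 of 76) for 56/28 and 58% (44 of 76) for 110/55, ignoring completion at failure or at 180 days in place. Survival therefore needs its own follow-up rule.

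**The case against.** The best defence is that the sentence in 3.4 lists the two dates that settle the primary endpoint and was not meant to end all follow-up. Section 7.1 keeps patients on study for more than 180 days after removal, and staff may look up deaths in any case. The objective is only to record survival, and section 6.0 plans no comparison of it by arm. This carries weight on intent, but both texts are current, no other provision covers survival after removal, and the schedule repeats the narrower rule.

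Several stronger readings are tempting, and the documents do not support them.
- A reader might count only deaths with the catheter in place, giving 38 × (0.199 + 0.111) = 12 deaths, or 38 × (0.328 + 0.196) = 20. The rule starts only after week 10, and serious adverse event capture runs later still, so these counts are too low.
- A reader might set them against nearly all 76 deaths. Any real cut-off leaves some patients alive, hence 54 to 59.
- A reader might infer that follow-up ends early for the patients doing best. Removal for infection, blockage, pain or a dislodged cuff ends it too, so the direction of any bias is not established. The independence assumed in the arithmetic does not address it either.
- A reader might call a survival comparison biased and almost empty. The plan contains no such comparison and no censoring rule, and every patient still contributes follow-up time.
- That most deaths go unseen is an inference from the design medians. The preliminary series shows 29 of 58 catheters removed because they were no longer needed, and a confidence limit of 328 days.

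**Conclusion.** The contradiction holds on the text alone. Following 3.4 and the schedule as written, secondary failure, pleurodesis success and completion at more than 180 days after removal cannot be ascertained, and overall survival has no follow-up after removal. The length of survival follow-up would then depend on the primary event and, if valproate shortens time to removal, on arm.

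Under the assumptions above, about 18 to 22 deaths (56/28 days) or 24 to 27 (110/55 days) would be recorded, against roughly 54 to 59 by a cut-off 3 to 6 months after the last enrolment. The loss is smaller if catheters stay in longer. The primary endpoint is untouched, because removal and death with the catheter in place are both captured. This should be corrected because a named secondary objective and the 7.1 outcomes depend on it.

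**What to change.** Amend the passage in 3.4 on evaluations beyond week 10, and the record-review row of the Study Parameters table, so that review continues for every randomised patient whether or not the catheter has been removed and whatever the reason for removal:
- for date of death, or date last known alive, to a stated data cut-off;
- for re-drainage of the affected side, to 180 days after removal, in line with 7.1.

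Add a sentence to 6.0 saying that any survival summary by arm runs from randomisation and censors at the date last known alive or the cut-off, not at catheter removal. State also that meeting a completion criterion in 7.1 does not end the review for date of death.

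The cost is additional chart review by existing staff, with no new visits or procedures. It is a cheap improvement.
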